### **Cohort Expansion (Part C)**

The objective of this expansion in combination with nivolumab is to support further clinical testing by demonstrating adequate safety and tolerability as well as favorable benefit-risk by assessing preliminary efficacy measured by ORR and other clinically relevant efficacy measures such as DOR and DCR. However, the sample size is strictly based on efficacy, specifically based on the target ORR relative to historic ORR.

Disease- and prior IO therapy-restricted cohorts will be investigated in the Part C cohort expansion: NSCLC progressing on IO therapy; melanoma progressing on anti-PD-1/anti-PD-L1; RCC naive to IO therapies; NSCLC naive to IO therapies; melanoma first line; SCCHN naive to IO therapies; gastric cancer naive to IO therapies; HCC naive to IO therapies; and bladder (urothelial) cancer naive to IO therapies. The NSCLC progressing on IO therapy cohort will be analyzed as a whole and as 2 separate subgroups, refractory and relapsed, as defined in [Section 3.3.1](#). All disease cohorts will be handled independently, and there will be no multiplicity adjustment.

A multistage design will be used as a guide for each expansion cohort in order to decide whether the treatment of BMS-986016 in combination with nivolumab warrants more extensive development. At first, a 2-stage design with a reasonable false positive rate (eg, < 10%) and false negative rate (eg, < 10%) will be used for the decision making based on assumptions of true (target) and historic/standard-of-care response rate for each cohort. The assumed historic and target response rates may change over time and may need to be adjusted by the time of response data from this study are available. Using a 2-stage design provides an option to stop early for futility as well as a signal of preliminary antitumor activity for strong-go early on. Enrollment may continue into Stage 2 while the planned number of subjects for Stage 1 is followed for efficacy-evaluable tumor assessments. There will be no stopping of a disease cohort for efficacy, although early plan for the next stage of clinical development may be initiated.

The ORRs considered to be of clinical value for further expansion of selected populations, sample size, and operational characteristics of using a 2-stage design, as an example, are provided in [Table 3](#), although this is not for statistical hypothesis testing.

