### **1.1.6      *Rationale for Part D Expansion***

As of the cutoff date of 15-Jun-2017, preliminary proof-of-concept efficacy has been revealed in the Part C combination treatment expansion cohort of advanced melanoma with prior treatment with anti-PD-1/PD-L1. All subjects were treated with BMS-986016 80 mg + nivolumab 240 mg every 2 weeks (Q2W). The overall ORR was 11.5% (7/61 response evaluable), with a disease control rate (DCR) of 49%. Biomarker analyses suggested that subjects whose TIL expressed more LAG-3 had a higher response rate, with a greater than 3-fold increase in ORR observed in subjects with evidence of LAG-3 expression in at least 1% of nucleated cells within the tumor margin,

compared with less than 1% LAG-3 expression (18.2% [6/33] and 5.0% [1/20], respectively). PD-L1 expression did not appear to enrich for response. The treatment group had the following characteristics: 1) most subjects had M1C disease (68%), 2) the cohort was heavily pretreated (77% with 2 or more prior therapies and 57% with prior anti-CTLA-4 therapy), 3) all subjects had progressed while receiving anti-PD-1/PD-L1, and 4) progressive disease (PD) was the best response to prior anti-PD-1/PD-L1 in 46% of subjects. Overall, anti-LAG-3 (BMS-986016) in combination with nivolumab demonstrated encouraging initial efficacy with a safety profile similar to nivolumab monotherapy.

Based on initial efficacy signal in advanced melanoma subjects who progressed on anti-PD-1/PD-L1 therapy, additional subjects in this subset population for further clinical testing are justified. Assessment in this population will be extended in 2 subparts: Part D1 and D2. D1 will test the combination in a focused eligibility population, whereas D2 will allow assessment in a broader population under expanded eligibility criteria.

Given the improved response rate in subjects whose tumor-associated immune cells express more LAG-3, efficacy analysis in Part D1 will be the primary focus. Subjects whose tumors are LAG-3 negative will also be evaluated to determine the role of LAG-3 expression on the antitumor activity of BMS-986016. Part D2 will explore safety and efficacy in a broader patient population, including those with Eastern Cooperative Oncology Group performance status (ECOG PS) up to 2 and among those with a more diverse set of prior therapies.

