### **1.1.9 Rationale for Dose Selection**

CA224020 currently consists of 6 parts. Part A and Part B consist of a 3 + 3 + 3 dose escalation design and, implemented in site-specific amendment #15 (dated 13 August 2018) and superseding the 3 + 3 + 3 dose escalation design, the Bayesian Logistic Regression Model (BLRM)-Copula design, with BMS-986016 administered as a single agent (Part A) or in combination with nivolumab as sequential infusion (Part B) in subjects with advanced solid tumors. Part A1 consists of expansion cohorts of approximately 6 to 12 subjects in each disease-restricted population, with BMS-986016 monotherapy. Part C consists of expansion cohorts of approximately 25 to 40 subjects each in disease-restricted populations (and further expansion of up to approximately 90 to 120 subjects in selected cohorts based upon safety and efficacy profiles), with BMS-986016 administered in combination with nivolumab as sequential infusions. Part D consists of advanced melanoma subjects with progression on prior anti-PD-1 therapy enrolled into 2 subgroups based upon eligibility criteria. Part E consists of both melanoma participants who experienced disease progression on prior anti-PD-1 therapy and melanoma participants who have not received prior systemic anticancer therapy for unresectable or metastatic melanoma. The sequential infusion of BMS-986016 and nivolumab will be administered in Parts A, A1, B and C. In Part D, subjects will be administered BMS-986016 and nivolumab coadministration or BMS-986213 (fixed-dose combination [FDC] relatlimab/nivolumab at a 1:3 ratio in a single vial). In Part E, subjects will be administered BMS-986016 and nivolumab as a coadministration. See [Section 4.1.1](#) for details.

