#### **8.1.3 *Cohort Expansion (Part C)***

The objective of this expansion in combination with nivolumab is to support further clinical testing by demonstrating adequate safety and tolerability as well as favorable benefit-risk by assessing preliminary efficacy measured by ORR and other clinically relevant efficacy measures such as

DOOR and DCR. However, the sample size is strictly based on efficacy, specifically based on the target ORR relative to historic ORR.

Disease- and prior IO therapy-restricted cohorts will be investigated in the Part C cohort expansion: NSCLC progressed on IO therapy; melanoma progressed on anti-PD-1/anti-PD-L1; RCC naive to IO therapy; NSCLC naive to IO therapy; melanoma first line; SCCHN naive to IO therapy; bladder naive to IO therapy; gastric cancer naive to IO therapy; and HCC naive to IO therapy. The NSCLC progressing on IO therapy cohort will be analyzed as a whole and as 2 separate subgroups, refractory and relapsed, as defined in [Section 3.3.1](#). All disease cohorts will be handled independently, and there will be no multiplicity adjustment.

A multistage design will be used as a guide for each expansion cohort in order to decide whether the treatment of BMS-986016 in combination with nivolumab warrants more extensive development. At first, a 2-stage design with a reasonable false positive rate (eg, < 10%) and false negative rate (eg, < 10%) will be used for decision making based on assumptions of true (target) and historic/standard-of-care response rate for each cohort. The assumed historic and target response rates may change over time and may need to be adjusted by the time of response data from this study are available. Using a 2-stage design provides an option to stop early for futility as well as a signal of preliminary antitumor activity for strong-go early on. Enrollment may continue into stage 2 while the planned number of subjects for Stage 1 are followed for efficacy evaluable tumor assessments. There will be no stopping of a disease cohort for efficacy, although early plan for the next stage of clinical development may be initiated.

The ORRs considered to be of clinical value for further expansion of selected populations, sample size, and operational characteristics of using a 2-stage design, as an example, are provided in Table 8.1.3-1, although this is not used for statistical hypothesis testing.

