**Table 8.1.3-1: Example of a 2-stage Design Characteristics**

Cohort	Historic/ Target Rate (%)	Stage	Cum. Sample Size	Conclude Futility if R a	Conclude Efficacy if R	PET b or Futility (%)	PEE c or Efficacy (%)
Gastric IO naive							
HCC IO naive	10/30	1	15	≤ 1	≥ 4	55	70
		2	26	≤ 5	≥ 6		
Melanoma progressed on anti-PD-1/PD-L1							
RCC IO naive	25/50	1	11	≤ 2	≥ 6	46	50
		2	26	≤ 9	≥ 10		
NSCLC IO refractory	5/20	1	12	0	≥ 3	54	44
NSCLC IO relapsed		2	37	≤ 3	≥ 4		
NSCLC	20/45	1	14	≤ 3	≥ 7	70	45

**Table 8.1.3-1:** Example of a 2-stage Design Characteristics

Cohort	Historic/ Target Rate (%)	Stage	Cum. Sample Size	Conclude Futility if R a	Conclude Efficacy if R	PET b or Futility (%)	PEE c or Efficacy (%)
1/2L, IO naive		2	25	≤ 7	≥ 8		
Melanoma		1	13	≤ 5	≥ 10		
1L	40/65	2	28	≤ 14	≥ 15	57	28
SCCHN							
IO naive		1	20	≤ 4	≥ 8		
Bladder	20/40	2	36	≤ 10	≥ 11	63	58
IO naive							

a R is the cumulative number of responses at the end of stage.

b PET: probability of early termination.

c PEE: probability of early expansion.

Once there is preliminary evidence of the treatment effect that may represent substantial improvement over available therapies, sufficient additional subjects will be treated to demonstrate a substantial and clinically meaningful effect in ORR that is supported by duration of the effect. The total sample size at this stage will be determined based on the ability to produce a CI, which would exclude an ORR of the historic response, and to provide sufficient information for a reliable understanding of the safety profile. With 90 to 120 subjects in total, this design yields a less than 5% 2-sided type I error rate and at least 80% power depending on tumor type with specified historic/standard of care and target rates. [Table 8.1.3-2](#) summarizes the 95% exact CI for various observed ORRs with sample sizes of 90, 100, and 120.

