## APPENDIX 7 REvised Protocol Summary of Change History

### Overall Rationale for Protocol Amendment 14, 28-Oct-2022

The CA224020 study started with the first patient enrolled on 01-Nov-2013 and is closed to enrollment as of 30-Jul-2021 with the last patient enrolled on 30-Jul-2021.

The purpose of this protocol amendment is to clarify the study duration for patients remaining on treatment beyond 5 years, remove the rechallenge period among patients currently on the study, align the protocol with the current coronavirus disease 2019 (COVID-19) guidance, and update the contraceptive guidance.

Currently, study duration is defined as approximately 5 years from the first dose of study drug including 5 years of follow-up for survival and will remain as such except for those patients who remain on treatment beyond 5 years and are still deriving clinical benefit. Patients who discontinue treatment before 5 years will complete a 135-day clinical follow-up period and a survival follow-up period for up to 5 years after the first dose. Patients who continue study treatment for longer than 5 years will complete a 135-day clinical follow-up period once the criteria for treatment discontinuation are met, but will not participate in a survival follow-up period. The study will end when all patients have completed their respective follow-up periods.

Current literature is not sufficient to give clear recommendations on the clinical utility of immunotherapy rechallenge. Furthermore, data concerning rechallenge utilizing combination treatments from randomized cohorts with similar clinical characteristics is limited or missing. Given the lack of rechallenge data from randomized clinical trials, no standardized approach exists; however, the current practice is to switch therapies upon progression. Given this limited data and [REDACTED], the decision was made to suspend future participation in the rechallenge period. All subjects who discontinue primary study treatment following implementation of this amendment will not be eligible for rechallenge. Subjects currently receiving rechallenge treatment will be allowed to continue, and subjects currently in the rechallenge-eligible Survival Follow-up as of this Protocol Amendment remain eligible for rechallenge.

Summary of Key Changes for Protocol Amendment 14		
Section Number & Title	Description of Change	Brief Rationale
Synopsis	Incorporates changes below as applicable.	Updated to reflect study changes.

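### The printed 10/30 two-stage rule for Part C has an overall false-negative rate of about 14%, not the illustrative < 10% given in Section 8.1.3

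*Combined protocol and SAP*

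**What the plan says.** Section 8.1.3 describes the first step of the Part C multistage design as a two-stage design with a "reasonable false positive rate (eg, < 10%) and false negative rate (eg, < 10%) will be used for decision making", given assumed historic and target response rates for each cohort. The synopsis section on Part C has almost the same sentence: "reasonable false positive rate (eg, < 10%) and false negative rate (eg, < 10%) will be used for the decision making".

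The rules are in Table 8.1.3-1, titled "Example of a 2-stage Design Characteristics" (synopsis Table 3). For each historic/target pair the table gives the cumulative sample size, the futility and efficacy counts at each stage, the PET and the PEE. It has no column for the overall false-positive or false-negative rate. Section 8.1.3 says of the table: "although this is not used for statistical hypothesis testing". It also says that the assumed rates may need adjusting over time.

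The plan words Stage 1 futility in two ways. Sections 3.1 and 3.1.2.2 say that cohorts judged futile at Stage 1 will be discontinued. The worked RCC example in Section 8.1.3 says only that such a cohort may be stopped.

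**The concern.** A reader who sees the < 10% sentence next to the table will take it that each printed rule has both error rates under about 10%. PET and PEE do not allow that to be checked, because they describe Stage 1 alone. The table guides which tumour cohorts expand and which are dropped. If a rule misses an active treatment more often than the text suggests, a decision to drop a cohort under it is weaker evidence of inactivity than a reader would assume.

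**Working it through.** **Inputs (Table 8.1.3-1; responses are cumulative).**

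| Historic/target | Stage 1 n: futile / go | Stage 2 n: futile / go |
|---|---|---|
| 10/30 | 15: ≤1 / ≥4 | 26: ≤5 / ≥6 |
| 25/50 | 11: ≤2 / ≥6 | 26: ≤9 / ≥10 |
| 5/20 | 12: 0 / ≥3 | 37: ≤3 / ≥4 |
| 20/45 | 14: ≤3 / ≥7 | 25: ≤7 / ≥8 |
| 40/65 | 13: ≤5 / ≥10 | 28: ≤14 / ≥15 |
| 20/40 | 20: ≤4 / ≥8 | 36: ≤10 / ≥11 |

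**Step 1: reproduce the plan's figures.** By exact binomial, PET = P(X1 ≤ futility cut) at the historic rate and PEE = P(X1 ≥ go cut) at the target rate. In the order above, PET is 54.9, 45.5, 54.0, 69.8, 57.4 and 63.0%; PEE is 70.3, 50.0, 44.2, 45.4, 27.8 and 58.4%. All twelve round to the printed values, so the rules have been read as intended.

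**Step 2: overall go probability.** With Stage 1 futility binding and a Stage 1 go counted as a go,

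P(go) = P(X1 ≥ e1) + Σ P(X1 = x) · P(X2 ≥ e − x), summed over futility cut < x < e1,

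where e1 and e are the Stage 1 and final go cuts. The false-positive rate (FP) is P(go) at the historic rate. The false-negative rate (FN) is 1 − P(go) at the target rate.

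For 10/30, Stage 2 adds 26 − 15 = 11 subjects, and only x = 2 or 3 continues.

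- At 30%: 0.7031 + 0.0916 × 0.4304 + 0.1700 × 0.6873 = 0.7031 + 0.0394 + 0.1169 = 0.8594, so FN = 14.06%.
- At 10%: 0.0556 + 0.2669 × 0.0185 + 0.1285 × 0.0896 = 0.0556 + 0.0049 + 0.0115 = 0.0720, so FP = 7.20%.
- The 14.06% splits into 3.53 points from Stage 1 stops (≤1 of 15 at 30%) and 10.53 points from failing at Stage 2.

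**Step 3: all six rules under the four readings.** The futility cut may be binding or not, and a Stage 1 go may end the decision or not. Entries are FP/FN in %.

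| Rule | Binding, early go | Non-binding, early go | Binding, no early go | Non-binding, no early go |
|---|---|---|---|---|
| 10/30 | 7.20/14.06 | 7.30/13.38 | 3.89/16.94 | 3.99/16.26 |
| 25/50 | 9.96/9.49 | 10.48/7.97 | 8.57/9.95 | 9.09/8.43 |
| 5/20 | 9.83/9.67 | 11.67/4.41 | 9.35/9.76 | 11.19/4.50 |
| 20/45 | 9.41/9.71 | 10.99/6.36 | 9.33/9.74 | 10.91/6.39 |
| 40/65 | 9.45/9.60 | 10.40/7.31 | 9.30/9.65 | 10.25/7.36 |
| 20/40 | 9.03/10.70 | 9.78/8.65 | 8.14/11.09 | 8.89/9.04 |

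For 10/30, FN is above 13% in every column. For 20/40, it passes 10% only in the two binding columns. In the first column the other four rules have both errors between 9.4% and 9.96%. That pattern suggests, as an inference, that 10% was the working limit and that the first column is the reading the designers used.

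**The case against.** The strongest reply is that nothing printed is wrong and no commitment is broken. The limit is given as an example of a reasonable rate, the table is an example and a guide, the assumed rates may move, and expansion rests on all available data rather than on the response count alone. All of this stands, and it is why the point is minor. It does not make the sentence true of the 10/30 rule, which misses by about 4 points where four other rules sit just inside the limit.

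Three stronger readings are tempting and are not supported.

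- *That 20/40 plainly fails as well.* It does so only if Stage 1 futility is binding, and the plan's wording supports both readings. An excess of 0.7 to 1.1 points over an illustrative limit, under one reading, is borderline.
- *That the error rates drift further because cohorts may run to other sizes.* Section 1.1.9 says "Part C consists of expansion cohorts of approximately 25 to 40 subjects each in disease-restricted populations", and Section 8.1.3 says "Enrollment may continue into stage 2 while the planned number of subjects for Stage 1 are followed for efficacy evaluable tumor assessments". The first fits a summary across cohorts of the printed Stage 2 totals, which run from 25 to 37. The second concerns overlap of the stages, not going past the planned total. Nothing says that a final cut of 6 would be kept at another sample size.
- *That an active cohort was wrongly dropped.* The documents do not say whether the gastric or HCC cohort was dropped at either stage. The melanoma cohort went well past 26 subjects: "The overall ORR was 11.5% (7/61 response evaluable".

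Assigning gastric, HCC and melanoma to the 10/30 rule rests on the table's layout.

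**Conclusion.** The point holds, at minor severity. The < 10% description in Section 8.1.3 and the synopsis does not fit the printed 10/30 rule. Its overall FN is about 14% (13.4% to 16.9% across readings), power is about 86%, and FP is about 7% (about 4% if a Stage 1 go does not end the decision). The 20/40 rule is borderline and depends on whether Stage 1 futility binds.

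The 14% is the rate for the whole rule, over both stages, at the printed sample sizes and a true response rate of 30%, with the count alone deciding. It should not be read as the error attached to a Stage 2 futility conclusion by itself. Since the study "is closed to enrollment as of 30-Jul-2021", what remains is how the rule is described and how any dropped 10/30 cohort is reported.

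**What to change.** Add overall FP and FN columns to Table 8.1.3-1 and synopsis Table 3. Add a footnote stating the assumption: Stage 1 futility binding, and a Stage 1 go counted as a go. The assumption is needed because, with non-binding futility and an early go, four rules have FP of 10.4% to 11.7%. The entries (FP/FN, %) are:

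- 10/30: 7.2/14.1
- 25/50: 10.0 (9.96 unrounded)/9.5
- 5/20: 9.8/9.7
- 20/45: 9.4/9.7
- 40/65: 9.5/9.6
- 20/40: 9.0/10.7

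In Section 8.1.3 and the synopsis, replace the blanket < 10% with a sentence such as: *Under this assumption the false-negative rate is about 14% for the 10/30 rule, about 11% for the 20/40 rule and below 10% for the other example rules; the false-positive rate is below 10% for all six.*

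If a 10/30 cohort was dropped at either stage, the report should give the rule's overall FN as about 14% (about 3.5 points from Stage 1 stops and 10.5 points from Stage 2), not as < 10%.

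The cost is two columns and a footnote in two tables, and one sentence in two places. No threshold, sample size or enrolment changes. The disclosed false-negative rates for 10/30 and 20/40 will look less favourable.

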**Table 8.1.3-1: Example of a 2-stage Design Characteristics**

Cohort	Historic/ Target Rate (%)	Stage	Cum. Sample Size	Conclude Futility if R a	Conclude Efficacy if R	PET b or Futility (%)	PEE c or Efficacy (%)
Gastric IO naive							
HCC IO naive	10/30	1	15	≤ 1	≥ 4	55	70
		2	26	≤ 5	≥ 6		
Melanoma progressed on anti-PD-1/PD-L1							
RCC IO naive	25/50	1	11	≤ 2	≥ 6	46	50
		2	26	≤ 9	≥ 10		
NSCLC IO refractory	5/20	1	12	0	≥ 3	54	44
NSCLC IO relapsed		2	37	≤ 3	≥ 4		
NSCLC	20/45	1	14	≤ 3	≥ 7	70	45

**Table 8.1.3-1:** Example of a 2-stage Design Characteristics

Cohort	Historic/ Target Rate (%)	Stage	Cum. Sample Size	Conclude Futility if R a	Conclude Efficacy if R	PET b or Futility (%)	PEE c or Efficacy (%)
1/2L, IO naive		2	25	≤ 7	≥ 8		
Melanoma		1	13	≤ 5	≥ 10		
1L	40/65	2	28	≤ 14	≥ 15	57	28
SCCHN							
IO naive		1	20	≤ 4	≥ 8		
Bladder	20/40	2	36	≤ 10	≥ 11	63	58
IO naive							

a R is the cumulative number of responses at the end of stage.

b PET: probability of early termination.

c PEE: probability of early expansion.

Once there is preliminary evidence of the treatment effect that may represent substantial improvement over available therapies, sufficient additional subjects will be treated to demonstrate a substantial and clinically meaningful effect in ORR that is supported by duration of the effect. The total sample size at this stage will be determined based on the ability to produce a CI, which would exclude an ORR of the historic response, and to provide sufficient information for a reliable understanding of the safety profile. With 90 to 120 subjects in total, this design yields a less than 5% 2-sided type I error rate and at least 80% power depending on tumor type with specified historic/standard of care and target rates. [Table 8.1.3-2](#) summarizes the 95% exact CI for various observed ORRs with sample sizes of 90, 100, and 120.

Guided by [Table 8.1.3-1](#) initially, approximately 11 RCC subjects, for example, will be treated in Stage 1. Assuming the true response rate is 50% when treated with BMS-986016 in combination with nivolumab, if there are 6 or more responses in 11 subjects, it may be decided to expand further up to approximately 90 subjects in total after careful evaluation of all available data, including DOR and safety profile. The probability of early decision to expand further for efficacy is approximately 50% if, in fact, the treatment is efficacious. If there are 2 or fewer responses in 11 treated subjects, the cohort may be stopped for futility. The probability of early stopping for futility is approximately 46% if, in fact, the treatment is inefficacious, eg, 25%. If there are 3 to 5 responses, an additional 15 subjects may be treated to collect more data. At the end of Stage 2, if there are 10 or more responses, an additional 64 subjects may be treated up to a total of 90 subjects. [Table 8.1.3-2](#) shows that at observed ORR  $\geq 36\%$ , the lower bound of the 95% CI excludes 25% with a sample size of 90.

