#### **8.4.2 Efficacy Analyses**

Individual BOR, DOR, and PFS will be determined based on RECIST v1.1 criteria for the primary and secondary analyses. iRECIST will be used as an exploratory analysis in Parts C and D. BOR outcomes will be summarized using frequency tables together with 2-sided 95% CIs. Time to event distribution (eg, PFS and DOR) will be estimated using the Kaplan-Meier method. When appropriate, the median along with 95% CI will be provided using Brookmeyer and Crowley methodology (using log-log transformation for constructing the CIs). Rates at fixed time points (eg, PFS rate 24 weeks) will be derived from the Kaplan-Meier estimate, and corresponding CI will be derived based on Greenwood formula. CIs for binomial proportions will be derived using the Clopper-Pearson method. OS data will be analysed similarly to PFS data analysis.

For the purpose of demonstrating preliminary clinical evidence of the treatment effect in advanced melanoma subjects who progressed while on receiving anti-PD-1 antibody therapies, the primary efficacy population will be subjects with LAG-3 expression who progressed while on anti-PD-1 antibody therapies in Part D1-Q2W. A portion of subjects in Part C who meet the eligibility criteria of Part D1 will be included in the sensitivity analysis to further strengthen the evidence. Efficacy analysis will also be performed for subjects with a lack of LAG-3 expression, and also for all treated subjects regardless of LAG-3 expression to support the treatment effect of the combination therapy.

Initial cutpoint for the purpose of exploring an enriched population is LAG-3 expression  $\geq 1\%$ . However, as the optimal marker cutpoint is not well known prior to the study, several different cutoffs may be explored other than the initial cutpoint of 1% by examining receiver operating characteristics curves using the ORR, although the decision of the cutpoint will be based on the totality of the efficacy data, including DOR and DCR. Details of methodology will be described in the statistical analysis plan prior to any data exploration in Part D.

In an effort to explore an enriched patient population in advanced melanoma subjects who progressed while on anti-PD-1 antibody therapies in Part D1, other potential predictive markers such as BRAF mutation status may be explored.

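### Part C: the ORR of a cohort expanded after a response gate pools the gate subjects without adjustment, so on average it reads high, mainly when the true rate is near the historic rate; a post-gate sensitivity estimate should be added

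*Combined protocol and SAP*

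**What the plan says.** Section 8.1.3 guides each Part C disease cohort through a two-stage response rule (Table 8.1.3-1) and then, if the signal is good, up to 90-120 subjects. In the RCC example, "if there are 6 or more responses in 11 subjects, it may be decided to expand further up to approximately 90 subjects in total"; with 3 to 5 responses the cohort goes to 26 subjects, and then "if there are 10 or more responses, an additional 64 subjects may be treated up to a total of 90 subjects". So 26 + 64 = 90, or 11 + 79 = 90: the subjects who opened the gate are part of the final sample.

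The final size is "determined based on the ability to produce a CI, which would exclude an ORR of the historic response". The section adds: "With 90 to 120 subjects in total, this design yields a less than 5% 2-sided type I error rate and at least 80% power". It illustrates the criterion with 32 of 90 responses, where the exact lower limit clears the 25% historic rate. Section 8.4.2 fixes the interval method: "CIs for binomial proportions will be derived using the Clopper-Pearson method". Neither section gives an estimate or interval that allows for the gate.

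Section 8.1.3 also calls the multistage design a guide and the table an example outside hypothesis testing. It rules out stopping a cohort for efficacy and makes no multiplicity adjustment across cohorts.

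**The concern.** A cohort reaches 90 subjects because its first subjects responded well. Part of that early success is chance, and those same subjects are counted again in the reported ORR. An interval built for a fixed sample of 90 does not know this. The readers of a 90-subject Part C result see only cohorts that passed the gate, so for them the relevant properties are those given expansion.

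Part C ORR is a coprimary endpoint (8.3.1), and 8.1.3 presents the expanded cohort as the evidence for a substantial effect. If the pooled figure leans upward by a few points when the drug adds nothing, that should be visible in the report.

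**Working it through.** **Inputs.** From Table 8.1.3-1: historic rate p0, target rate p1, Stage 1 size n1 with its futility and expansion cut-offs, Stage 2 size n2 with its cut-off. Final N = 90. Interval: two-sided 95% Clopper-Pearson. The gates are treated as binding.

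**Reproducing the plan (RCC, 25%/50%).** P(R ≤ 2 of 11 at 25%) = 45.5% and P(R ≥ 6 of 11 at 50%) = 50.0%, matching the printed 46% and 50%; the other five rules also reproduce. The exact lower limit is 24.7% at 31/90 and 25.7% at 32/90, so the cut-off is 32. Without a gate, the error at 25% is P(X ≥ 32) + P(X ≤ 14) = 1.67% + 2.18% = 3.84%, and power at 50% is 99.8%.

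**Error of the whole design.** With no efficacy stop, a claim needs both expansion and X ≥ cut-off, so P(expand and X ≥ c) ≤ P(X ≥ c). For RCC at 25% it is 0.84%, against 1.67% without the gate. Overall power across the six rules is 85.9-90.4% at N = 90. The stated limits hold.

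**Bias given expansion (RCC, true rate 25%).**
- Through Stage 1: probability 0.0343, mean 6.26 responses of 11, expected 11 × 0.25 = 2.75, excess 3.51.
- Through Stage 2: probability 0.0653, mean 10.58 of 26, expected 6.50, excess 4.08.
- P(expand) = 0.0343 + 0.0653 = 0.0996.
- Mean excess = (0.0343 × 3.51 + 0.0653 × 4.08) / 0.0996 = 3.88 responses.
- Bias = 3.88 / 90 = 4.3 points; mean pooled ORR 29.3%.
- P(X ≥ 32 given expansion) = 0.845% / 9.96% = 8.5%. Coverage is 91.5%.

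**All six rules, N = 90, true rate = historic rate** (exact enumeration of Stage 1, Stage 2 and the added subjects):

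| Historic/target (%) | P(expand) | Expand and exclude | Bias, points | Exclude, given expansion | Coverage, given expansion |
|---|---|---|---|---|---|
| 10/30 | 7.2% | 0.68% | 3.3 | 9.4% | 90.6% |
| 25/50 | 10.0% | 0.84% | 4.3 | 8.5% | 91.5% |
| 5/20 | 9.8% | 0.89% | 2.8 | 9.1% | 90.9% |
| 20/45 | 9.4% | 0.77% | 4.1 | 8.2% | 91.8% |
| 40/65 | 9.5% | 1.07% | 5.1 | 11.3% | 88.7% |
| 20/40 | 9.0% | 0.94% | 4.9 | 10.4% | 89.6% |

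A plain sample of 90 would exclude the historic rate from above in 1.4-2.1%. At N = 120 the bias is 2.1-3.9 points and exclusion given expansion 6.8-9.8%.

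**At better true rates (N = 90, given expansion).** Midway between historic and target: bias 1.2-2.3 points, coverage 95.2-97.5%. At target: bias 0.4-0.6 points, coverage 96.2-97.2%.

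**Post-gate subjects only (N = 90).** The post-gate sample is 90 − n1 or 90 − n2, that is 53 to 79 subjects. Given expansion, the exact interval excludes the historic rate in 1.4-2.4% when that rate is true, and in 92-99% at target. Midway it excludes in 39-66%, against 74-88% for the pooled interval.

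**The case against.** Three stronger readings are tempting, and the documents support none of them.

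First, a reader might infer that the claim "With 90 to 120 subjects in total, this design yields a less than 5% 2-sided type I error rate" is wrong. It is not. The claim is made for the design, and a gate that can only remove claims lowers the error. If all ten disease rows were at their historic rates, about 0.88 cohorts would expand and 0.08 would falsely exclude, against 0.16 with no gate.

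Second, a reader might infer that every expanded cohort reports a materially inflated ORR with a failing interval. The bias is an average over expanded cohorts, is small at the target rate, and comes with undercoverage only near the historic rate; a cohort at that rate expands only 7-10% of the time.

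Third, a reader might conclude that the historic-rate criterion should move to the post-gate interval. That would give up much sensitivity at intermediate rates to control an error already below nominal overall.

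The other side also has the plan's framing. The gates are a guide, expansion follows a review of all data, and sections 1.2 and 8.5 disclaim formal inference. So the figures describe strict use of the printed gates. Discretion does not remove the selection, since expansion is still tied to good early response; it makes its size harder to state. For the melanoma prior-IO signal, the plan already separates the data: Part D1 subjects are the primary efficacy population, and eligible Part C subjects enter only a sensitivity analysis (8.1.4.1, 8.4.2). The documents do not say that any Part C cohort was expanded to 90-120 under these gates.

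**Conclusion.** The point holds as a reporting gap, not a design failure. The stated error and power are right. What is missing is any allowance, or any disclosure, for the fact that a 90-120 subject ORR exists only because the cohort's early responses were favourable. Near the historic rate that matters by about 3 to 5 points of ORR at N = 90, with exclusion of a true historic rate in roughly one expanded cohort in ten; at the target rate it is negligible.

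These sizes rest on the Table 8.1.3-1 gates applied as printed, a fixed N chosen at the gate, and independent responses with a constant rate. The plan allows historic and target rates to be revised, which would change the gates and the figures.

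**What to change.** In 8.1.3 and 8.4.2, with matching synopsis text:

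- Keep the pooled ORR and Clopper-Pearson interval as the main result for an expanded Part C cohort.
- For each cohort taken past a Stage 1 or Stage 2 gate, add a prespecified sensitivity analysis: the ORR with exact 95% CI in the subjects not counted in R at that gate, or a two-stage bias-adjusted estimate.
- Define the gate set by subject, because enrolment may continue into Stage 2 while Stage 1 is being followed.
- State that the error rate below 5% refers to all cohorts started, not to cohorts given that they expanded.

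The cost is one extra row per expanded cohort and a few sentences, with no change to design or enrolment. The post-gate interval is wider: by the normal approximation at a 50% rate, 1.96 × √(0.25/n) is 10.3 points at n = 90 and 13.5 at n = 53. It is also less sensitive at intermediate rates, so it belongs beside the pooled interval and should not become the decision criterion.
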